QT interval will be measured on an ongoing basis through day 10 via the Zio AT mobile cardiac telemetry device describe in section 4.7 E. If the corrected QT - QTc interval increases from baseline of > 60msec or QT > 500 msec, the medications, if still being taken, will discontinued at that time. Participant QTc intervals will be monitored every 6 hours until the interval returns to baseline. If a serous arrhythmia is detected during the continuous monitoring, the study cardiologist and participant will be promptly contacted, and the participant will be directed to seek medical treatment as appropriate.

C. Study Safety Assessments

The Principal Investigator is responsible for ensuring that all staff involved in the study are familiar with the content of this section.

- 1. Definitions:
 - Adverse Events:

An adverse event is the development of an undesirable medical condition or the deterioration of a pre-existing medical condition following or during exposure to a pharmaceutical product, whether considered causally related to the product. An undesirable medical condition can be symptoms (e.g., nausea, chest pain), signs (e.g., tachycardia, enlarged liver), or the abnormal results of an investigation (e.g., laboratory findings, electrocardiogram). In clinical studies, an AE can include an undesirable medical condition occurring at any time, including run-in or washout periods, even if no study treatment has been administered. The term AE is used to include both serious and non-serious AEs.

• Serious Adverse Events:

A serious adverse event is an AE occurring during any study phase (i.e., screening, runin, treatment, wash-out, follow-up), at any dose of the study drugs that fulfills one or more of the following criteria:

- Results in death
- Is immediately life-threatening
- Requires in-patient hospitalization or prolongation of existing hospitalization
- Results in persistent or significant disability or incapacity

- Is a congenital abnormality or birth defect
- Is an important medical event that may jeopardize the patient or may require medical intervention to prevent one of the outcomes listed above.
- The causality of SAEs (their relationship to all study treatment/procedures) will be assessed by the investigator(s) and communicated to the FDA via MedWatch form, if applicable.
- 2. Recording of Adverse Events

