Non-serious adverse events and SAEs will be determined from the time the study drug is given, throughout the treatment period and up to and including the one month follow-up period. All grade 3 or higher AEs will be recorded. Grade 1 - 2 AEs do not need to be recorded. After withdrawal from treatment, participants must be followed-up for all existing and new AEs for 60 calendar days after the last dose of trial drug and/or until event resolution. All new AEs occurring during that period must be recorded (if SAEs, they must be reported to Data Safety Monitoring Board (DSMB) and Rutgers IRB as per SOPs.).

All study-related toxicities/ SAEs must be followed until resolution, unless in the Treating Investigator's opinion, the condition is unlikely to resolve due to the patient's underlying disease.

3. Reporting of Serious Adverse Events

Investigators and other site personnel must inform the DSMB and Rutgers IRB. FDA will be informed as required accordance with the reporting obligations of 21 CFR 312.32. It is the responsibility of the principal investigator to compile all necessary information and ensure that the FDA receives a report according to the FDA reporting requirement timelines.

All SAEs meeting the criteria for expedited reporting will be reported to the Rutgers IRB within the mandated time frames. All SAEs within the safety follow-up window (e.g., within 30 days after the last dose of study medications) established in the protocol will be reported.

- 4. Clinical Safety Assessments
 - Recording of Adverse Events

Non-serious adverse events and SAEs will be determined from the time the study drug is given, throughout the treatment period and up to and including the 28-day follow-up period. All grade 3 or higher AEs will be recorded. Grade 1-2 AEs do not need to be recorded. After withdrawal from treatment, participants must be followed-up for all existing and new AEs for 28 calendar days after the last dose of trial drug and/or until event resolution. All new AEs occurring during that period must be recorded (if SAEs, they must be reported to the Data Safety Monitoring Committee and Rutgers IRB).

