- 4. Proportion of participants with progression of severity of COVID-19 symptoms (hospitalization and length of stay; admission to intensive care unit and number of days in unit; Intubation; Death (any cause))
- 5. Comparison of severity of disease in participants who develop symptoms of COVID-19 at all timepoints
- 6. Assessment of medication toxicity as measured by standard metrics
- 7. Q-T interval from baseline of > 60msec or QT > 500 msec)
- 8. Number of participants with undetectable viral load and absence of symptoms
- 9. Rate of decline in viral load at study days 3 and 6
- 10. New, self-reported COVID infection in household members

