Once participants are started on study drug, monitoring for prolongation of QTc or development of polymorphic ventricular tachycardia is required. The Zio AT (iRhythm Technologies, Inc.) is a mobile cardiac telemetry device that allows continuous monitoring of the QTc interval and heart rhythm abnormalities. The Zio AT consists of a small transdermal patch that is applied on the participant's upper chest and a gateway device (size of a cell phone) that has to be kept within 10 feet of the participant. The ECG signal is transmitted to iRhythm technologies via the internet using the gateway. The participant does not have to change batteries or do anything to the device for the 10-day monitoring interval. We have used this device clinically and participant compliance is excellent. The rhythm is monitored continuously for arrhythmias and our EP-cardiology team will be notified immediately for any run of ventricular tachycardia (VT) greater than 4 complexes and other significant arrhythmias (pauses greater than 3 seconds, heart block, atrial fibrillation). We are monitoring for any run of VT since we have found that most episodes of torsade de pointes VT are preceded by shorter runs of polymorphic VT. The participant can also

trigger a transmission by pressing a small button on the transdermal patch if they experience any cardiac symptoms. We will monitor the QTc with this device. We will obtain a baseline transmission at the initial visit after the participant has been deemed to be eligible based on the Kardia Mobile 6L QTc measurement. We will ask the participant to do a transmission for QTc measurement 2 hours after the first dose of study drug. These will be reviewed and QTc measured by our EP cardiology team. We will then monitor the QTc interval twice a day at two predetermined times. This type of monitoring is equivalent to what can be done in the hospital on telemetry and in practice may be superior since the protocol will be strictly adhered to and measurements made by an electrophysiologist. If QT interval increases from baseline of > 60msec or QT > 500 msec, the medications, if still being taken, will discontinued at that time. Participant QT will be monitored every 6 hours until the interval returns to baseline. If a serous arrhythmia is detected during the continuous monitoring, the study cardiologist and participant will be promptly contacted, and the participant will be directed to seek medical treatment as appropriate.

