6.0 Data Management Plan

6.1 Data Analysis

We will follow intention-to-treat principles and analyze the groups as randomized. A summary table of baseline variables will be created with means and standard deviations for continuous variables or percentages for categorical variables, all stratified by treatment group.

Primary outcome. We will have repeated measures of log10 VL for each participant. These measurements will occur on day 0 (baseline) and at about days 3, 6 and 10. We will fit a linear mixed effects model, where log10 VL is the outcome, indicators for treatment group (SoC reference), time, and treatment by time interactions are the predictors. The model will include a random slope and intercept, to account for within participant correlation. The robust sandwich variance will be used to estimate standard errors. Because we are estimating within participant changes over time from randomization, we can estimate a treatment effect at any particular day. Our primary hypotheses involve the change over time, which we will assess with the treatment by time interaction terms. If participants drop out from the study

before the day 10 visit, we will use all of their preceding data. Linear mixed effects models rely on the assumption that missing data are missing at random.

Secondary outcomes. For binary outcomes, such as progression to having symptoms, intubation, death, hospitalization, and admission to intensive care unit, we will fit logistic regression models. The covariates will include the treatment group indicators. We will report odds ratios and 95% confidence intervals. For change variables, such as change in viral shedding or change in Q-T interval, we will fit linear mixed effects models (similar to primary outcome).

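### A ventricular tachycardia run during dosing that is judged non-serious and grade 1–2 has no required route to the database, the DSMB halfway review or the side-effect comparison

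*Combined protocol and SAP*

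**What the plan says.** Section 4.7 E states that "monitoring for prolongation of QTc or development of polymorphic ventricular tachycardia is required" once study drug has started. Telemetry runs for 10 days, and "our EP-cardiology team will be notified immediately for any run of ventricular tachycardia (VT) greater than 4 complexes". The reason given is the team's own experience that "most episodes of torsade de pointes VT are preceded by shorter runs of polymorphic VT". For a serious arrhythmia the stated response is clinical: the cardiologist and the participant are contacted, and the participant is directed to care.

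Section 1.3 C defines an adverse event to include symptoms, signs "or the abnormal results of an investigation (e.g., laboratory findings, electrocardiogram", so a VT run on telemetry qualifies. On recording it says "All grade 3 or higher AEs will be recorded. Grade 1 - 2 AEs do not need to be recorded", and repeats the rule under Clinical Safety Assessments. It adds that after withdrawal from treatment all new adverse events must be recorded.

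Section 1.3 F lists ten secondary endpoints. Endpoint 7 is "Q-T interval from baseline of > 60msec or QT > 500 msec"; endpoint 6 is "Assessment of medication toxicity as measured by standard metrics". None names VT or arrhythmia. Section 6.1 says "For change variables, such as change in viral shedding or change in Q-T interval, we will fit linear mixed effects models", and its examples of binary outcomes do not include arrhythmia. Section 6.3 B has the DSMB review reported adverse events and their incidence when half the participants are enrolled.

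**The concern.** By the protocol's own reasoning, a short polymorphic run is the warning sign that the telemetry is there to find. Such a run may cause no symptoms and may be judged non-serious. The participant cannot report a run that was not felt, and adverse event review on days 3, 6 and 10 is by telephone, so the alert may be the only evidence of it.

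Section 1.7 records ventricular arrhythmias and torsades with hydroxychloroquine, and section 1.4 says that this triple combination has never been used in humans. The cardiology team can protect the individual who triggers an alert. Seeing whether alerts cluster on active drug is a separate task, and it needs the alerts as data. Because low-grade events may be left out, the DSMB and the final report could lack that information although the team received every alert.

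**Working it through.** The plan gives no figure for VT, so the first check follows each required monitoring target through the text.

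| Step | QT | VT |
|---|---|---|
| Monitoring required (4.7 E) | Yes | Yes (polymorphic) |
| Row in the schedule of events (1.3 A) | Yes | No |
| Named in the data points (1.3 D) | No | No |
| Named secondary endpoint (1.3 F) | Yes, endpoint 7 | No |
| Named in the analysis (6.1) | Yes | No |
| Named in the DSMB report (6.3 B) | No | No |

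Endpoint 7 obliges the trial to hold QT data even though the data-point list omits QT. No comparable obligation exists for VT, which leaves adverse event reporting:

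- VT judged serious: reported as an SAE to the DSMB and IRB.
- VT of grade 3 or higher: recorded.
- VT arising after withdrawal from treatment: recorded as a new adverse event.
- VT during dosing, non-serious and grade 1–2: recording not required. The protocol names no grading scale, so the grade of a short run is left open.

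**What complete recording would give.** Planned telemetry is 70 × 10 = 700 participant-days. With zero alerts in n participants, the one-sided exact 95% upper bound is 1 − 0.05^(1/n):

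- n = 35 (the active arm): 1 − 0.05^(1/35) = 8.2%.
- n = 17 (about half of the 35 enrolled at the halfway review): 1 − 0.05^(1/17) = 16.2%.

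With 0.025 in place of 0.05, as in a two-sided exact 95% interval, the limits are 10.0% and 19.5%. None of these bounds can be stated if low-grade alerts may be missing.

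**Illustration of loss.** The documents give neither an alert rate r nor a share s of alerts that are grade 1–2 and left out, so both are assumed. The chance that at least one alert reaches the data is 1 − (1 − r(1 − s))^n.

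| n | r | s = 0 | s = 50% | s = 75% | s = 90% |
|---|---|---|---|---|---|
| 35 | 2% | 50.7% | 29.7% | 16.1% | 6.8% |
| 35 | 5% | 83.4% | 58.8% | 35.6% | 16.1% |
| 35 | 10% | 97.5% | 83.4% | 58.8% | 29.7% |
| 17 | 5% | 58.2% | 35.0% | 19.3% | 8.2% |

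A smaller omitted share does less harm: with n = 35, r = 5% and s = 25%, the chance is 73.8%.

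**What a test between arms could show.** At 35 per arm with no placebo events, the two-sided Fisher p-value for k active events is 2 × C(35,k)/C(70,k).

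- k = 5: 2 × 324,632/12,103,014 = 0.054.
- k = 6: 2 × 1,623,160/131,115,985 = 0.025.

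Significance therefore needs 6 versus 0. The binomial chance of 6 or more among 35 is 0.7% at a 5% alert rate and 13% at 10%.

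**The case against.** The strongest reply is that the run that matters most is also the one most likely to be captured. The SAE definition includes important medical events that may jeopardize the patient, and a polymorphic run regarded as a torsade precursor may well meet it. That stands, and it confines the gap to runs that the investigator judges non-serious and low grade. Seriousness is a case-by-case judgement, however, and the protocol does not say that a short run qualifies.

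A reader might infer that low-grade events are barred from recording, or that the adverse event form is the only way in. The documents support neither reading. The grade rule is permissive. Section 6.2 says that eCRFs hold data from protocol procedures, and telemetry is one. Section 1.3 D refers to a data capture plan that is not part of these documents. Section 1.9 B allows care records to be abstracted with permission. These are possible routes, but none names VT alerts and none requires them to be entered.

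The sentence on new events after withdrawal from treatment also counts. It covers anyone taken off drug; whether it covers everyone once dosing ends on day 5 is arguable. It does not clearly reach the dosing days.

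Section 6.3 B commits the investigators to give the DSMB sufficient safety information and allows expanded ad hoc reporting. Expansion follows an unexpected safety concern, though, and alerts that are not recorded may never raise one.

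Finally, pauses, heart block and atrial fibrillation also trigger notification and also lack endpoints. That is fair: the root of the problem is the general grade threshold, and VT is where it matters most.

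**Conclusion.** The point holds in a limited form and is a cheap improvement. A VT run during dosing that is judged non-serious and grade 1–2 has no required route to the database, the DSMB halfway review or the side-effect comparison. This follows from the text and rests on no assumed rate.

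The firm numbers are the zero-event bounds, 8.2% with 35 active participants and 16.2% with 17, which are available only if all alerts are recorded. The capture percentages are illustrative because the alert rate and grade mix are assumed.

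A reader might infer that the trial would miss dangerous arrhythmias, or that recording every alert would permit a reliable test between arms. The first is not supported: serious and grade 3 or higher VT is captured, and the cardiology team receives every alert for a run over 4 complexes. The second fails on the Fisher calculation, so the counts should be reported descriptively. Whether study drug should be held after a VT alert is a clinical trade-off and no part of this point.

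**What to change.** 1. In section 1.3 C, exempt telemetry alerts from the grade threshold. Every VT alert to EP-cardiology (more than 4 complexes) is entered in the eCRF whatever its grade, with date, run length, morphology (polymorphic or not), QTc at the time and study-drug action.
2. Beside endpoint 7 in section 1.3 F, with a matching line in section 6.1, report the number and proportion of participants with any VT alert through day 10, by arm, with exact 95% intervals and labelled descriptive.
3. In section 6.3 B, add these counts to the DSMB halfway report.

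The cost is one short form, one reporting line, one row in the DSMB table and a few minutes of staff time per alert. The alerts already reach the cardiology team, so no new device or visit is needed. The primary analysis is unchanged.

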 - Arm 1: NTZ 1000 mg (2 x 250 mg tablets BID for day one) and then 1000 mg (2 x 250 mg tablets BID for 4 days) RBV 1200 mg (3 x 200 mg capsules BID day one) and then RBV 800 mg (2 x 200mg capsules BID for 4 days) HCQ 800 mg (2 x 200 mg tablets bid day one) and then HCQ 400 mg (1 x 200 mg tablet BID for 4 days)
 - Arm 2: Placebo for NTZ (2 tablets BID for day one and then 2 tablets BID for 4 days) Placebo for RBV (3 capsules BID day one and then 2 capsules BID for 4 days) Placebo for HCQ (2 tablets bid day one and then 1 tablet BID for 4 days)

Hydroxychloroquine sulfate (HCQ)

One hydroxychloroquine sulfate tablet contains 200 mg of hydroxychloroquine sulfate, which is the equivalent to 155 mg base.

Ribavirin (RBV)

One ribavirin capsule contains 200 mg of ribavirin.

Nitazoxanide (NTZ)

One nitazoxanide tablet contains 500 mg of nitazoxanide.

Take all tablets/capsules with a meal or a glass of milk.

All study drugs should be stored at room temperature 20°-25° (68°-77 °F).

Concomitant Medications & Supportive Guidelines

Study participants can receive full supportive care therapies concomitantly during the study. We will advise rest, fluids, hot/ showers/baths. We will recommend NO antipyretics since they make infections worse by interfering with the generation of fever--which is considered beneficial until it reaches 102 degrees F.

B. Participant Enrollment

We will identify asymptomatic or mildly symptomatic participants who test positive for SARS-CoV-2 from the Rutgers Coronavirus Cohort (RCC) and hospital screening programs, or from the community through advertisements at our medical center, university, and in local publications. The recruiting materials will direct the potential participants to online materials that include information about the trial, consent forms, and a screener questionnaire to assess eligibility. If eligible for the trial, we will answer any questions and provide as much time as needed to review all study materials. The participant may then electronically sign the consent or, as an alternative, wait until the initial visit to re-review and sign the consent. The consenting process will be primarily performed remotely to protect research personnel.

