As soon as possible after consent, the participant will participate in an in person visit for baseline biospecimen collection. On arrival, research staff wearing PPE will re-review the consent, confirm/obtain signatures, measure the PO2, do a urine pregnancy test in women with potential to be pregnant and measure the baseline QTc interval with the Kardia Mobile 6L (AliveCor, Inc). A 6 lead EKG is obtained when the patient places their fingers on 2 electrode sensors while holding

the device on their leg. The ECG is uploaded to an iPhone and the tracing is sent to the Electrophysiologist cardiologist who will calculate the QT and QTc. The device is approved by the FDA for QTc measurements. The participant will be excluded if the Q-T interval is prolonged beyond 450 Msec. We will also exclude anyone who has a PO2<92% or a positive pregnancy test. We will randomly allocate the participant, provide the assigned medications, and obtain mid-turbinate self nasal swab and blood samples. We will also take the participant's temperature and pulse. We will provide education to the patient on how to complete all at-home study procedures and use all ancillary study supplies which we will provide (self nasal swab specimen kits, thermometer, and pulse oximeter).

We will telephone the participant about 2 hours after the initial medication dose to confirm that the Zio AT patch has been triggered for the one-time 2 hour reading (see the Risks of Harm/Potential for Benefits to Subjects to Subjects section, page 35), review the BID dosing schedule, study procedures, and any participant questions. We will also call on days 3, 6, and 10 for procedure review and to confirm self- specimen collection and AE review. We will have an in person visit on day 14 to collect a blood specimen and on day 28 to collect a blood specimen and urine pregnancy test, review medical status and AEs Self collection of mid-turbinate nasal swab to measure viral shedding will be on days 3, 6 and10 post randomization.

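### The QT stopping rule is written as QTc in one section and raw QT in another, and the two versions can give opposite decisions on the same tracings

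*Combined protocol and SAP*

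**What the plan says.** The discontinuation rule appears twice.

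- Section 1.3 B (Participant Enrollment): "If the corrected QT - QTc interval increases from baseline of > 60msec or QT > 500 msec", followed by "Participant QTc intervals will be monitored every 6 hours until the interval returns to baseline".
- Section 4.7 E (Minimizing Risks of Harm): "If QT interval increases from baseline of > 60msec or QT > 500 msec", followed by "Participant QT will be monitored every 6 hours until the interval returns to baseline".

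For the readings themselves, section 4.7 E asks for QTc two hours after the first dose, and then: "We will then monitor the QTc interval twice a day at two predetermined times". At baseline, section 1.3 B sends the tracing to a cardiologist "who will calculate the QT and QTc", so both quantities are available.

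Secondary endpoint 7 (section 1.3 F) reads "Q-T interval from baseline of > 60msec or QT > 500 msec". The mixed model in section 6.1 also refers to change in the Q-T interval, with no mention of correction. The entry limit of 450 ms is QT in section 1.3 B but QTc in exclusion criterion 12 (section 4.1 C). No correction formula is named anywhere.

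**The concern.** This rule decides when a participant stops a regimen containing hydroxychloroquine, which section 1.7 says prolongs the QT interval, with torsades de pointes reported. Doses are self-administered at home for five days. If one section tests QTc and the other raw QT, the same pair of tracings can mean stop under one and continue under the other.

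Raw QT shortens as heart rate rises, so a raw limit of 500 ms is too permissive above 60 bpm and too strict below it. Heart-rate shifts are plausible in this population. Section 1.3 accepts fever as a mild entry symptom, and its supportive-care guidance says: "We will recommend NO antipyretics since they make infections worse by interfering with the generation of fever".

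The ambiguity also reaches the analysis. If endpoint 7 and the section 6.1 model use raw QT, heart-rate changes add noise and false threshold crossings in both arms.

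**Working it through.** The plan gives no figure to reproduce. The check is a comparison of wording, followed by an illustration of how far the two versions can diverge.

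**Wording**

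| Element | Section 1.3 B | Section 4.7 E |
|---|---|---|
| 60 ms rise | QTc | QT |
| 500 ms limit | QT | QT |
| 6-hourly recovery monitoring | QTc | QT |
| Scheduled on-treatment reading | QT, deferring to 4.7 E | QTc |

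The two sections contradict each other on the first and third rows. On the 500 ms limit they agree with each other and with endpoint 7. There the mismatch is with the quantity that 4.7 E schedules.

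**Formulas.** RR = 60/HR. Fridericia: QTc = QT/RR^(1/3). Bazett: QTc = QT/RR^(1/2). The documents name neither formula and give no heart-rate distribution. The formulas, heart rates and QTc starting values below are therefore illustrative assumptions.

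1. *1.3 B stops, 4.7 E continues.* QTc goes from 420 ms at 65 bpm to 485 ms at 90 bpm, a rise of 65 ms.
   - Fridericia raw QT: 420 × (60/65)^(1/3) = 408.9 ms; 485 × (60/90)^(1/3) = 423.7 ms; change about +15 ms.
   - Bazett raw QT: 403.5 to 396.0 ms; change -7.5 ms.

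2. *4.7 E stops, 1.3 B continues.* QTc stays at 420 ms while heart rate falls.
   - Fridericia, 100 to 62 bpm: raw QT 354.2 to 415.4 ms, +61.2 ms.
   - Bazett, 100 to 71 bpm: raw QT 325.3 to 386.1 ms, +60.8 ms.

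3. *The 500 ms limb.* QTc when raw QT is exactly 500 ms:

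| Heart rate | Fridericia | Bazett |
|---|---|---|
| 50 bpm | 470 ms | 456 ms |
| 80 bpm | 550 ms | 577 ms |
| 100 bpm | 593 ms | 645 ms |

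   Under 1.3 B the 60 ms QTc limb catches most of these first. Entry QTc is at most 450 ms, so that limb acts by 450 + 60 = 510 ms. The raw 500 ms limb then matters mainly for baselines of 440 to 450 ms. Example (Fridericia): QTc from 445 to 503 ms is +58 ms. At 90 bpm, raw QT is 503 × (60/90)^(1/3) = 439.4 ms. Neither version stops drug, provided the baseline rate was about 96 bpm or less.

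4. *Choice of formula.* Raw QT of 400 ms at 100 bpm is 400/0.6^(1/3) = 474.3 ms (Fridericia) or 400/0.6^(1/2) = 516.4 ms (Bazett). These fall on opposite sides of 500 ms.

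5. *Endpoint.* At QTc 420 ms and 75 bpm, raw QT moves by QT/(3 × HR) = 389.9/225 = 1.73 ms per bpm (Fridericia) or QT/(2 × HR) = 375.7/150 = 2.50 ms per bpm (Bazett). If mean heart-rate change is equal between arms, the bias is 0. For an assumed 5 bpm difference it is 8.7 or 12.5 ms.

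**The case against.** The best defence is that QT is shorthand for QTc. The paragraph in 4.7 E opens by requiring monitoring for QTc prolongation, every reading it schedules is QTc, and the stopping sentence follows shortly after. Section 1.3 B says QTc expressly for the 60 ms limb. The screening text in 4.1 C also runs the two terms together. This is plausible, and an electrophysiologist reading the tracings would probably apply QTc. But the protocol never states the shorthand. Section 1.3 B uses both terms in one sentence and has both calculated at baseline. A stopping rule should not depend on staff overriding its words.

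Other points stand in part:

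- The large QTc values in step 3 apply only if 4.7 E is followed literally. Under 1.3 B the gap is about 500 to 510 ms.
- A stop caused only by a falling heart rate (step 2) errs on the safe side for the participant.
- Step 4 tests a QTc limit of 500 ms that the protocol does not contain. It shows why a formula must be named, not an error in the existing limb.
- Section 4.7 E also provides continuous rhythm monitoring, immediate notification of ventricular tachycardia runs above 4 complexes, and participant-triggered transmissions. These reduce the risk but do not settle which QT quantity triggers stopping.
- The endpoint 7 text ends in an unmatched bracket, so words may have been lost. The endpoint argument is secondary and rests equally on section 6.1.

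**Conclusion.** The concern holds. The 60 ms limb and the recovery monitoring contradict each other between sections 1.3 B and 4.7 E. The 500 ms limb names a quantity other than the one scheduled for measurement on treatment. No formula is given. These are facts of the text and need no assumption.

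How often the versions would disagree cannot be computed, because the documents give no heart-rate data. The examples show that opposite decisions arise from rate shifts of about 25 to 40 bpm between baseline and follow-up. The arm comparison on QT is biased only if heart-rate change differs by arm; otherwise raw QT adds noise. Because this is a drug-discontinuation threshold, it should be treated as a required correction even if it began as loose drafting.

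**What to change.** Use QTc with one pre-named formula throughout, for example Fridericia, confirmed by the study cardiologist. In both 1.3 B and 4.7 E, write the rule as: *study medications are discontinued if QTc rises by more than 60 ms from baseline or exceeds 500 ms; QTc is then measured 6-hourly until back to baseline.* Use the same quantity and formula in secondary endpoint 7 (1.3 F) and in the section 6.1 model. Align the 450 ms entry sentence in 1.3 B with exclusion criterion 12, which already says QTc.

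The cost is wording only. QTc is already measured at baseline, two hours after the first dose and twice daily, so no new readings or equipment are needed.
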